In order to address Aim 4 and evaluate the impact of posttraumatic stress symptoms on contextual processing, we include the following online-only sub-study.

Following a within-subjects study design, up to 500 adult participants, between 18 and 89 years, will be asked to complete experimental tasks that assesses configural and elemental contextual learning and memory. The 89-year age cut-off is used to avoid data collection of age being a HIPAA identifier. For example, participants will see different images of virtual rooms that include arrangements of common household furniture (e.g., couch, table, rug, plant). Over time participants will learn that certain objects (e.g., plant) or furniture configurations (e.g., white couch on left plus plant in foreground) are associated with the presence of a “bomb” in specific rooms by showing them an image of an explosion on the next screen. After learning, contingency ratings will be obtained by asking participants whether they think a bomb is present in various virtual rooms and how certain they are on a sliding scale.

Participants will also be asked to state their age (in years), sex assigned at birth (male/female), and complete questionnaires assessing the presence of symptoms related to PTSD (e.g., PTSD Checklist for DSM-5 (PCL-5)), depression (e.g., Patient Health Questionnaire depression scale (PHQ-8)), and anxiety (e.g., Generalized Anxiety Disorder 7-item scale (GAD-7)). Additionally, random attention checks using “catch” items will be included throughout the experiment. An example of such an item is “Please select ‘yellow’ out of the following options: a) yellow, b) blue, c) red, d) green.”

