It should be noted that we will not be able to review answers to questions in real-time. As such, we are not able to detect participants who might be at (higher) risk for self-harm. For that reason, we will list the phone number and URL for SAMHSA’s National Helpline – [name] and <https://www.samhsa.gov/find-help/national-helpline> – at the bottom of each page when participants are completing the above-listed questionnaires as well as at the end of the study on a thank you-page. SAMHSA is “a free, confidential, 24/7, 365-day-a-year treatment referral and information service (in English and Spanish) for individuals and families facing mental and/or substance use disorders.” Given that we will limit our recruitment to individuals residing in the USA only, providing SAMHSA’s contact information will be appropriate. Additionally, because we will not directly interact with online participants and collect only the minimum amount of data to answer our research question, we will not know whether online participants might be pregnant or are justice-involved. However, based on the above outlined online study procedures we do not anticipate the protection of these vulnerable subjects is affected (e.g., study coercion is low if there is no interaction with the study team; materials and methods do not pose an additional risk for pregnant individuals).

Prolific (<https://www.prolific.co/researchers>) will be used to recruit online participants. Prolific is a panel-based platform on which individuals can create an account to participate in online research.

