Prolific's privacy policy meets the standards of the European, General Data Protection Regulation law (GDPR), and personally identifiable information from participants cannot and will not be collected through Prolific. More specifically, although Prolific will collect IP addresses, it is not possible for researchers to gain access to such or any personally identifiable data. Instead, participants have a Prolific ID that we will collect to provide reimbursement for study participation at a rate of \$8-\$16/hour (exact rate will depend on the complexity and length of individual tasks as well as Prolific's suggested rate) for a study duration of 60-90 minutes. Reimbursement occurs after the approval of study completion submissions by the research team. Although it is possible to reject submissions within 21 days of completion and forgo reimbursement to a participant, this is only allowed for pre-specified valid reasons (and Prolific may overturn rejections in certain occasions). In case of issues with participation, Prolific IDs can be used to contact participants through Prolific's email feature to protect the personal email addresses of both researchers and participants.

To run the experimental contextual learning and memory task as well as administer the questionnaires, Prolific will link to 'Pavlovia' and Brown University's instance of Qualtrics. Pavlovia is a place to run, share, and explore experiments online and which can run the 'PsychoPy' script of our experimental task, see also <https://pavlovia.org/docs/home/ethics>. Like Prolific, Pavlovia is GDPR compliant their server logs, which contain IP addresses, will not be shared with and cannot be accessed by the research team and will not be linked to participant data. The PsychoPy experimental script will automatically log the completion date of the experiment. Aside from this completion date no other personal identifiers will be collected. Questionnaire responses captured through Qualtrics will be collected in a fully anonymized manner, see <https://ithelp.brown.edu/kb/articles/use-qualtrics-for-human-subjects-research-anonymize-responses>.

4) REFERENCES

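### Online sub-study: the stated answer to undetectable self-harm risk is a referral helpline, with no stated instruction for a participant in immediate danger

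*Combined protocol and SAP*

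**What the plan says.** The section on the Aim 4 online sub-study states the limitation plainly: "we will not be able to review answers to questions in real-time", and so "we are not able to detect participants who might be at (higher) risk for self-harm". It gives this as the reason for listing the phone number and URL of one national helpline. These appear "at the bottom of each page when participants are completing the above-listed questionnaires" and again on the thank-you page. The protocol describes the helpline as "a free, confidential, 24/7, 365-day-a-year treatment referral and information service (in English and Spanish) for individuals and families facing mental and/or substance use disorders" and considers it suitable because recruitment is limited to US residents.

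The same section sets the conditions under which that contact operates:

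- Enrolment is "up to 500 adult participants, between 18 and 89 years".
- Staff are at a distance: "we will not directly interact with online participants".
- Answers cannot be traced to a person: "Questionnaire responses captured through Qualtrics will be collected in a fully anonymized manner".
- Messaging through the platform has a stated purpose: "In case of issues with participation, Prolific IDs can be used to contact participants".

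**The concern.** The protocol itself names the hazard as self-harm risk and presents the helpline as the response to it. A line that refers people to treatment is a sensible response to raised risk in general. It is a less obvious match for the acute end of that range, where someone may need help within minutes, and the section states nothing for that person.

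What is at stake is participant safety. With no live review and no staff contact, the on-screen text is the only safeguard this section states for self-harm risk. Participants are recruited across the range of PTSD symptoms. They answer questionnaires on PTSD, depression and anxiety, and the learning task shows them images of an explosion. The main study excludes people with acute suicidal ideation (section 3.A, exclusion criterion 3). The online section states no such exclusion; the limits it gives are age and US residence.

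**Working it through.** No arithmetic applies, and the plan gives no figure to reproduce. The check was to read the whole online sub-study section, list every safety provision it states, and compare the list with the provisions for the main study.

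**Step 1. Provisions stated in the online section**

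| Provision | Stated in the section? |
|---|---|
| Helpline phone number and URL | Yes, one helpline, on each questionnaire page and the thank-you page |
| Instruction to call emergency services | No |
| Suicide or crisis contact | No |
| On-call clinician or other staff-led safety route | No |

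That is 1 contact, 0 emergency instructions and 0 crisis contacts. The helpline's phone number has been removed from the public text; that is redaction and is not counted as a gap.

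**Step 2. Could another route described in the section fill the gap?** Three were considered:

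- Staff observation: ruled out, because staff have no direct interaction with participants.
- Follow-up of worrying answers: not provided for. Answers are not reviewed live, and the questionnaires are anonymised.
- Platform messaging: described for problems with taking part, not for safety.

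This leaves the on-screen text as the only stated safeguard.

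**Step 3. Comparison with the main study**

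| Setting | Stated emergency provision |
|---|---|
| Remote baseline (C3, Visit Day 1) | The participant's location is recorded so that a study clinician or emergency services can respond if suicidal intent is disclosed |
| Study sessions (D3, Data Safety Monitoring Plan) | The investigator or a designee contacts 911 and/or the university's EMS team in a medical emergency |
| Online sub-study | None stated beyond the helpline |

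The two main-study provisions are carried out by staff, so the online section does not contradict them. They do show that the plan already provides an emergency route where staff are present. Where no staff are present, the nearest equivalent is to give the instruction directly to the participant.

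**Step 4. Size.** The text would be seen by up to 500 people. That is an enrolment ceiling, not a count of people at risk. The documents give no rate of self-harm risk and no time spent on the questionnaires alone (the 60 to 90 minutes is for the whole session), so neither expected cases nor exposure time can be calculated.

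**The case against.** The strongest objection is that this is a claim of absence about material that is largely unseen. Section 2.A says the sub-study has its own consent form, and consent pages were removed from the public file. Emergency wording could well sit there or in the actual page text, which the protocol only summarises. This stands as a limit: it cannot be concluded that participants receive no such instruction anywhere. It does not remove the point. The section itself sets out what is shown on the questionnaire and thank-you pages, and a consent page read earlier does not put the instruction in front of someone at the moment of distress.

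A second objection is that the documents do not say how the helpline handles a caller in crisis, so calling it inadequate would need outside knowledge. That is correct, and no such claim is made. The point rests only on the difference between the hazard the protocol names and the service it describes.

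A third is that the risk has been recognised and met proportionately, that the main-study comparison involves clinical contact of a different kind, and that nothing in the documents says a questionnaire item asks about suicidal intent. Each of these is fair. They keep the point at the level of a suggestion. They do not explain what a participant in immediate danger is meant to do.

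**Conclusion.** The concern holds as a low-cost improvement to participant protection. The online section links undetectable self-harm risk to a single treatment referral and information contact, and states no emergency instruction or crisis contact for up to 500 unsupervised adults. It is not an inconsistency in the plan, and it does not affect sample size, error rates or any analysis.

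Confidence is medium. The conclusion assumes that the questionnaire and thank-you pages show what the section says they show and carry no unreported emergency wording. It makes no assumption about how many participants are at risk or how the helpline performs in a crisis.

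**What to change.** Keep the helpline where it is and label it as a treatment referral service. On the same questionnaire pages and the thank-you page, add a line such as: *If you are in immediate danger or thinking of harming yourself, call 911 or go to the nearest emergency department.* Beside it, show a US crisis contact agreed with the IRB. Use 911 and not the university EMS route from D3, because online participants may be anywhere in the USA.

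The cost is one or two lines of on-screen text and a minor IRB amendment. Data collection and analysis are unchanged.

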77. Loo, C. K., Martin, D. M., Alonzo, A., Gandevia, S., Mitchell, P. B., & Sachdev, P. (2011). Avoiding skin burns with transcranial direct current stimulation: preliminary considerations. *International Journal of Neuropsychopharmacology*, 14(3), 425-426

5) CRITERIA FOR WAIVER OF AUTHORIZATION FOR USE OF PROTECTED HEALTH INFORMATION (PHI)

5A. Does the requested use of PHI involve more than minimal risk to privacy?

YES *[if "YES," project is not eligible for PHI Waiver]* NO *[if "NO," address 1-3 below]*

1. Plan to Protect Patient Identifiers from Improper Use and Disclosure:

Potential risks due to loss of confidentiality will be minimized by having all information collected and handled by staff trained to deal appropriately with personal information. All research personnel will receive training in the protection of human research participants. All information will be treated as confidential information and be kept in locked file cabinets on-site. Computer data files will be available only to study personnel.

2. Plan to Destroy Identifiers or Justification for Retaining Identifiers:

After identification of potential participants and in the case (s)he does not want to participate, identifying information will be safely discarded per Butler Hospital procedures. When the person is interested in participating, identifiers will be retained so that they may be used for data analysis in this protocol and future investigations.

3. Assurances that the PHI will not be Re-used or Disclosed:

Information collected will only be used for purposes described below and will be treated as confidential. PHI collected as part of the study protocol will be shared only with collaborators and shared in de-identified form only. PHI gained from medical record searches will be specifically used to identify interested patient participants for the above-mentioned study. Potential participants will only be identified for the above-mentioned study.

5B. Could the research be practicably conducted without a waiver? YES NO

5C. Could the research be practicably conducted without access to and use of the PHI? YES NO

5D. PHI is only needed for activities preparatory to research YES NO

6) DESCRIPTION OF PHI TO BE COLLECTED UNDER WAIVER

To identify potential participants, we may need to review the medical records of patients at Butler Hospital either after potential participants reached out to us because they are interested in participating or because they take part in Butler Hospital clinics (e.g. Partial Hospital Programs/Women's Partial Program). This will involve their name, admitting information, treating clinician, and diagnosis. All PHI will be kept confidential within research team and clinic staff. Potential participants who are identified from reviewing the medical records of Butler Hospital clinics (e.g. Partial Hospital Programs/Women's Partial Program) will be given an outreach handout asking if they would be interested in participating/consent to being contacted. Medical records of participants who inquire about the study may be reviewed in order to confirm inclusion/exclusion criteria, and. PHI to be obtained includes patient demographic information (age, gender), contact information (name, phone number), treatment provider, and medical and treatment history.

7) ADVERTISEMENTS

ONLINE ADVERTISEMENT TEXT:

PROJECT RISE in PTSD

Research Investigating Stimulation for Extinction in PTSD

We are looking for people who are diagnosed by a clinician with posttraumatic stress disorder and who are interested in being part of a research study in which we look at the effects of a very low level of electrical current on the scalp (called tDCS) on emotional learning and memory. This study will involve four or five study visits. On the first visit we will do a screening and we might ask you to get a brain scan on a second visit. On visits three, four and five you will do a computer task that tests emotional learning and memory. During one of those days you may or may not also receive the very low level of electrical current through two electrodes attached to your head and may or may not also get a brain scan.

You may qualify if you:

- Are between 18-70 years-old
- Speak and read English fluently
- Have no history of closed-head injury or neurological disease
- Have no implanted electronic hardware, such as metal implants, pacemakers or medication pumps or metal in the head
- Have no current or history of psychosis or bipolar depression
- Have no holes in the skull made by trauma or surgery
- Have no history of epilepsy or seizures
- Are not pregnant

Number of visits: 4 or 5

Duration of visits: Visit 1 about 3 hours, visits 2-5 about 1 hour each visit.

[Participants will earn compensation for research participation.] or [Participants can earn up to \$170-\$270.]

If interested in learning more, please contact:

[Insert RA name]

Phone: [Insert study phone number]

8) INFORMED CONSENT FORM (ICF), ASSENT OF MINOR & PARENTAL PERMISSION FORM

See attached
